Self-Determination Inventory System - Parent version (SDIS): (Shogren et al., 2017) measures a parent/family member's perception of a young person's self-determination. This survey includes questions about goal-setting, decision-making, and choice-making skills. Parent participants use a sliding scale to indicate their level of agreement with various statements related to self-determination of their youth. The assessment comprises 22 items.	X			X		X

Open Ended Questions: Participants give their opinions on the intervention program and feedback for future changes.								X
---	--	--	--	--	--	--	--	---

- Notes: CI: Check-in FU: Comprehensive Follow-Up
- Outcome Key: ^T (=Intervention Target) ^P (=Primary) ^S (=Secondary)

6. Reporting of Adverse Events or Unanticipated Problems involving Risk to Participants or Others

Adverse events at any of the sites will be relayed immediately (within 24 hours of occurrence) to the VUMC PI and/or VUMC study coordinator by study staff at all sites. [name] [name] (VUMC PI) will be responsible for reporting any adverse event to the IRB within 7 calendar days from the day of report. If additional risks to participants are identified, then, [name] will disseminate information and guidelines to follow to the other participating sites. In addition, if data safety is compromised, the VUMC study coordinator will communicate with the other participating sites to provide guidance on what steps to follow to resolve or prevent the issue.

7. Study Withdrawal/Discontinuation

Participants may ask to withdraw from the study at any time with no penalty. If participants opt to withdraw for any reason at any point in the study, no further data collection will be conducted for that participant. Although the project is longitudinal, some of the analyses proposed involve data from only one time point; thus, early termination of a participant does not necessarily mean that his/her data cannot be included in the analyses. Records will be retained in instances of the early termination of a participant.

8. Statistical Considerations

Effects of the Intervention (Aims 1 and 2): Generalized linear models accounting for repeated measurements over time will be used to estimate the effect of treatment group assignment on each of the outcomes. In modeling, outcomes will be considered at their key time-points with treatment group and the interaction of treatment with time serving as the main explanatory variables. Such a model will allow us to test for differences between treatment and control groups over time while accounting for heterogeneity among subjects at baseline. While the randomized block design should minimize confounding, we will adjust for site and sex to improve precision. Regarding the choice of statistical model, we will use ordinary multiple regression for truly continuous responses, logistic regression for binary responses, and for outcome scales that are not truly continuous or have heavy ties in some of their values, the proportional odds ordinal logistic model. The error structure of the model is assumed to be compound symmetric, and the validity of this assumption will be examined by computing Akaike Information Criteria against other common structures. **Mediation (Aim 3):** To assess direct and indirect effects of potential mediator variables, we will follow steps outlined by MacKinnon and

colleagues to establish mediation. Mediation models will be estimated using the “mediation” package in R. **Moderation (Exploratory Aim 4):** Modifiers of treatment effect over time will be considered by introducing interactions between modifiers and the treatment by time interaction. The model building and validation strategy will otherwise be the same as for Aims 1 and 2.

Power/Sample Size: We plan to recruit 180 subjects and expect to retain 152 through the 12-month follow-up (76 per cohort). For power calculations, we consider baseline to post-test changes. For continuous outcomes, the size of effect that we will have 80% power to detect will be impacted by the correlation between the pre and post measurement of the outcome. At worst ($r=0$), we will have 80% power to detect a 0.46 sd difference in continuous outcomes. If the correlation is 0.2 or 0.4 we will be able to detect a 0.29 or 0.17 sd difference, respectively. We believe these estimates are conservative because, from our pilot work, correlations between baseline and post-test scores of intervention targets were 0.56 (empowerment), 0.39 (advocacy skills), and 0.57 (knowledge). For binary outcomes, the probability of being employed or in PSE was about 0.5 in pilot data; under this assumption we will have 80% power to detect a relative risk of 1.44. For Aim 4, we will have 80% power to detect a 0.42 sd modification of the treatment effect assuming a $r=0.2$. All calculations assume a two-sided significance level of 0.05. The power to detect **mediation effects** were made using the MedPow package in R. For the power calculation, we considered moderate associations between (1) VAP-T and the mediator ($r_{X,M}=0.3$), (2) Mediator and outcome, controlling for VAP-T ($r_{M,Y|X}=0.25$), (3) VAP-T and outcome controlling for the mediator ($r_{X,Y|M}=0.1$) using a fixed sample size of 152 ($\alpha=0.05$). Under these assumptions, we have 83% power to detect the indirect effect of VAP-T on the outcome through the mediator.

9. Privacy/Confidentiality Issues

IRB approval will be obtained prior to the initiation of the project. All project staff will be highly experienced in working with these populations, will have completed University mandated Human Subject Research Ethics training, and will be instructed in procedures for ensuring participant rights and confidentiality.

To protect confidentiality of participants, we will separate names and contact information from all other data. Participant codes, rather than names, will be used to index all data. Contact information, including names, must be maintained during this longitudinal study as participants must be scheduled for follow-up visits and all data files must be linked. Consent, contact information, and information linking participant identity with participant codes will be stored separately from all coded data.

Hard copies of data protocols will be stored in locked and secure cabinets accessible only to project staff. Electronic records with identifiers will be stored in a password-protected database. All lab personnel will be instructed as to the nature and confidentiality principles and procedures. The link between participant ID numbers and participant names will be destroyed when the project has been closed out with the IRB.

We will also video-/audio-record all the ADOS-2 administrations in their entirety (for visits before COVID-19 restrictions were established). This will allow us to perform fidelity checks and testing calibration. Parent and youth interviews completed during the baseline visit (Vineland 3, Vocational Index, Service Access Interview, and Goal identification) will be audio-recorded for reliability purposes. In addition, such recordings of sessions will allow us to re-score protocols that may need to be checked or that were difficult to score while they were being administered, and to complete the transcription and coding needed for the present project. As lead site for the project, the recordings will be centralized at VUMC. A secure cloud storage service such as Box/SharePoint/OneDrive will be used to safely transfer data in transit to the cloud with secure connections. Once stored on the cloud, data will be secured using file encryption. As an additional layer of security, users will receive a unique username and password to log into the service. Every effort will be made to ensure that the data is kept confidential.

A REDCap project created and managed by the VUMC research team will be used as a central location for data management. Vanderbilt University, with collaboration from a consortium of institutional partners, has developed a software toolset and workflow methodology for electronic collection and management of research and clinical trial data. REDCap (Research Electronic Data Capture) data collection projects rely on a thorough study-specific data dictionary defined in an iterative self-documenting process by all members of the research team with planning assistance from the VUMC PI and research coordinator. The iterative development and testing process result in a well-planned data collection strategy for individual studies. The REDCap system provides secure, web-based applications that are flexible enough to be used for a variety of types of research, provide an intuitive interface for users to enter data and have real time validation rules (with automated data type and range checks) at the time of entry. These systems offer easy data manipulation with audit trails for reporting, monitoring and querying patient records, and an automated export mechanism to common statistical packages (SPSS, SAS, Stata, R/S-Plus). REDCap servers are housed in a local data center at VUMC and all web-based information transmission is encrypted. REDCap was developed specifically around HIPAA-Security guidelines. REDCap has been disseminated for use locally at other institutions and currently supports 240+ academic/non-profit consortium partners on six continents and over 26,000 research end-users (www.project-redcap.org).

10. Follow-up and Record Retention

Data will be collected in Years 1-4 of the project. Hard copy materials with identifying information will be maintained (at each site) for 6 years after the closure of the study, then destroyed. All electronic files (de-identified data, video and audio recordings) will be kept indefinitely.

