Hypothesis. Relative to the materials-only control group, youth whose parents participate in ASSIST will have increased access to services and higher rates of employment, PSE, and social participation at 6-months and 12-months post-intervention.

Exploratory Aim 2a. We will examine whether ASSIST participation leads to enhanced goal attainment (as assessed by parents and youth with ASD), as well as better youth-reported quality of life and fit of employment/educational activities to the youth's skills and interests.

Exploratory Aim 2b. Using data collected 24-months and 30-months after intervention, we will examine whether treatment effects are maintained, strengthen, or wane.

Specific Aim 3. To examine which intervention targets (parent knowledge, advocacy skills, empowerment, advocacy activities) mediate the relations between ASSIST participation and youth outcomes of employment, PSE, social participation, service access, and goal attainment.

Hypothesis. In contrast to other intervention targets changed by ASSIST, parental empowerment will be the mechanism by which ASSIST participation leads to improvements in youth employment, PSE, social participation, service access, and goal attainment.

Exploratory Aim 4. To guide further adaptations of ASSIST, we will explore moderators of treatment response and barriers to participation in the intervention. We will explore factors that could relate to parents' ability to complete the ASSIST program and treatment

response, including: youth's intellectual functioning, pre- vs. post-high school exit, attendance at ASSIST sessions, socio-economic status, parental education, community size, family stress, and number of children with ASD in the family. We will also analyze qualitative data to inform future efforts to increase the accessibility of the ASSIST program for individuals with ASD.

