After eligibility is determined and baseline data are collected, parents will be randomized, in two cohorts, to the treatment or materials-only control condition. Given the relatively small sample size in each cohort at each site ($n = 30$ at each of three sites), simple randomization is not recommended as it might result in unequal group sizes. We will use 1:1 block randomization within each site to give an equal number of subjects in each group. To ensure balance of important covariates, we will block on our key moderators: whether the youth has an intellectual disability (ID) and is in high school. Co-occurring ID and being in vs. out of high school impact service eligibility, and ID impacts the likelihood of PSE and community employment. By balancing moderators, we maximize our power to detect effect modification of the treatment effect; and we minimize the chance of having a very extreme distribution of important (moderating) covariates.

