Autism Diagnostic Observation Schedule: (ADOS-2; Lord et al., 2012) A semi-structured standardized observational assessment of social interaction and communicative skills that was designed as a diagnostic tool for identifying the presence of autism. It is organized into four modules, which are distinguished by their appropriateness for use with individuals functioning at different developmental levels, ranging from nonverbal children to highly fluent adults. Each module provides a set of behavioral ratings in five domains: Language and Communication, Reciprocal Social Interaction, Play or Imagination/Creativity, Stereotyped Behaviors and Restricted Interests, and Other Abnormal Behaviors. We will mainly use Module 3 and 4 (dedicated to verbally fluent teenagers and adults), and Module 1 and 2 (that can be used for non-verbal adults or less verbal adults). The scoring algorithm provides cutoffs that can be used to discriminate between a diagnosis of autism, autism spectrum, or non-spectrum. The ADOS will be administered to participants with ASD. It will be administered by trained research staff. All ADOS-2 administrations will be video-recorded with the participant's explicit consent. Note: After data collection was moved online due to social distancing restrictions, the ADOS-2 was no longer required as a diagnostic measure for remaining participants.)	X		

Wechsler Abbreviated Scale of Intelligence (WASI-II, Wechsler, 2011): Provides a brief, reliable measure of cognitive ability for use in clinical, educational, and research settings. It is comprised of 4 subtests that yield a verbal intelligence quotient, a performance quotient, and an overall intelligence quotient. (Note: After data collection was moved online due to social distancing restrictions, the research staff used 2 of the subtests which were able to be administered virtually. The other 2 subtests were not administered to remaining participants.)	X		
Youth Measures (Longitudinal)	T0	T3	T6
Vocational - educational activities interview: ([name] & Seltzer, 2012) this instrument gathers information on vocational, educational, and other daytime activities. A trained research staff member will deliver this brief interview to gather information on current and previous high school employment, secondary education and post-high school vocational placements.	X	X	

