Exploratory Aim 4: The starting point for multivariable modeling is an additive effects model. A purely additive model, even one with allowance for flexible nonlinear relationships, will not fit adequately if interactive or synergistic effects exist. Empirical search for interactions is unreliable because there are too many possible interactions (product terms) and frequently interactions found by intensive search techniques are spurious. Instead, interactions will be pre-specified based on subject matter knowledge and all results reported, regardless of statistical significance. Separate models will be fit for each moderator by including an interaction between the potential moderator and the treatment by time interaction. A similar model fitting strategy as outlined for Aim 1 and Aim 2 will be followed.

Though we are interested in examining the potential role of race/ethnicity as a modifier, it may be difficult to disentangle the effects of race/ethnicity from study site (as the geographic area of each site has a different racial/ethnic make-up). We will examine cross tabulation tables of the association between race/ethnicity and

site to determine how strongly they are associated. If possible, we will examine race/ethnicity as a moderator.

We will present any race/ethnicity results cautiously and clearly indicate the associations with site that could confound the observed associations.

As part of Aim 4, we will also use qualitative data analysis to code information gained from the open-ended questions regarding ways to adapt the intervention for youth with ASD. All interviews will be recorded and transcribed verbatim. With Atlas-TI, emergent coding⁸⁷ and constant comparative analysis will be used to identify themes in the transcripts⁸⁸.

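### Randomisation is blocked on ID and high-school status, but the Aim 1 and 2 models adjust only for site and sex; the ID moderator also has no stated source, and the WASI-II changed form during enrolment

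*Protocol*

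**What the plan says.** **Randomisation.** Protocol section 4 (Randomization) describes 1:1 blocks within each site and adds: "we will block on our key moderators: whether the youth has an intellectual disability (ID) and is in high school". It gives the reason: both factors bear on service eligibility, and ID also bears on the chances of post-secondary education (PSE) and community employment. Baseline data are collected before parents are randomised. The section does not say how ID is determined.

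**Analysis.** Protocol section 8 and the SAP paragraph on Aims 1 and 2 both adjust for site and sex, to gain precision. Neither lists ID or high-school status as a covariate.

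**Moderation.** Exploratory Aim 4 in the Protocol lists "youth's intellectual functioning, pre- vs. post-high school exit" among its factors. The SAP says: "Separate models will be fit for each moderator by including an interaction between the potential moderator and the treatment by time interaction". It does not say whether intellectual functioning enters as a score or as ID yes/no, or where it comes from.

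**Cognitive test.** The Youth measures table in Protocol section 5 describes the WASI-II: "It is comprised of 4 subtests that yield a verbal intelligence quotient, a performance quotient, and an overall intelligence quotient". After the move online, "the research staff used 2 of the subtests which were able to be administered virtually", and "The other 2 subtests were not administered to remaining participants".

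**The concern.** A trial that constrains its allocation on a factor would normally carry that factor into the analysis. If it does not, the balance gained by blocking is not reflected in the standard error. In a linear model the reported uncertainty then tends to be too large for the design that was run. Here the Protocol itself argues that the omitted factors matter for the outcomes, so they are stronger candidates for adjustment than sex, for which it gives only a general precision argument.

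The moderator is a related gap. ID is called a key moderator, yet its operational definition is missing, and the only direct cognitive test in the schedule was shortened during enrolment. If a WASI-II score is the moderator, part of the sample has a score built from different content. The estimated interaction may then be diluted and harder to interpret.

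**Working it through.** **1. Blocking factors against model terms**

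| Factor | Used in randomisation (Protocol section 4) | In Aim 1 and 2 models (Protocol section 8; SAP) |
|---|---|---|
| Site | yes | yes, fixed effect, 2 d.f. |
| ID | yes | no |
| High-school status | yes | no |
| Sex | no | yes |

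Adding two binary blocks as main effects costs 2 d.f. among the 152 families expected at 12 months. If the blocks explain a share q of the residual variance of a continuous outcome, the standard error of a between-arm comparison is multiplied by about √(1 − q). The documents give no q, so the gain cannot be sized.

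**2. The plan's Aim 4 figure**

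Stated in the SAP: 80% power for a 0.42 sd modification, with r = 0.2, two-sided 0.05 and N = 152.

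- Base check, r = 0: (1.960 + 0.842) × 2/√152 = 0.454, or 0.457 with the t distribution. The plan states 0.46, so this agrees.
- Interaction per SD of a continuous moderator, adjusting for baseline: 0.454 × √(1 − 0.2²) = 0.445. This is not 0.42.
- Binary moderator split 50/50: 2 × 0.445 = 0.89.

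The 0.42 does not follow from the stated inputs under these formulas. Below it is only a reference point from which to measure relative loss.

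**3. Effect of the WASI-II change on a continuous-score interaction**

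Inputs:
- w, the share of families with two subtests. Baseline dates are not given. Protocol section 1.0 has the cohort 1 intervention groups in TN and IL starting in February 2020, before the pause. Baseline precedes randomisation, so those 2 × 30 = 60 families were clearly tested earlier. Hence w is at most (180 − 60)/180 = 67%. The lower end, 33%, is an assumption.
- ρ, the correlation between two- and four-subtest scores. This is not in the documents; 0.80 to 0.95 is assumed.

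Formula, for standardised scores with the four-subtest score as reference: a = (1 − w) + wρ. Power is Φ(2.802a − 1.960), and the detectable effect is 0.42/a.

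| w | ρ | a | Power, from 80% | Detectable, from 0.42 sd |
|---|---|---|---|---|
| 0.33 | 0.95 | 0.98 | 79% | 0.43 |
| 0.50 | 0.90 | 0.95 | 76% | 0.44 |
| 0.67 | 0.80 | 0.87 | 68% | 0.48 |

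**4. Arms**

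Testing comes before 1:1 allocation within site, so two-subtest families should be spread evenly over the arms.

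**The case against.** **On the covariates.** Leaving out the blocks does not bias the treatment effect, and the Protocol already relies on the blocked design for balance. That is right: the argument is about precision and consistency with the design. There is also a technical limit. In a random-intercept linear model with complete data, a time-constant covariate entered only as a main effect leaves the treatment-by-time estimate unchanged. To sharpen that contrast, the block effects must be allowed to vary with time. In the logistic and ordinal models, adjustment also changes the odds ratio from one averaged over the blocks to one within them. Both are reasons to write the terms carefully, not to omit them.

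**On the WASI-II.** A reader might infer several stronger claims that the documents do not support.

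- *The analysis pools the two forms.* The plan is silent. It never says that the WASI-II score is the Aim 4 moderator. Diagnostic information and the Vineland-3 are also collected at baseline, and ID could come from either.
- *Form goes with cohort, and so with in-person or web delivery.* Form follows baseline date. WI cohort 1 began ASSIST in August 2020, the same month as TN and IL cohort 2. No series was wholly in person; at most the TN and IL cohort 1 treated families, about 30 planned, had some in-person sessions.
- *ID status is badly misclassified.* If ID were cut from the WASI-II score, with assumed prevalence 25% to 35%, w of 0.50 to 0.67 and the same ρ, the multiplier would be about 0.71 to 0.90. Nothing says that ID was obtained in this way.
- *Less verbal youth drop out of the analysis.* Neither document says so.

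What survives is a specification gap in one exploratory interaction.

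**Conclusion.** The main point holds on the text alone: the trial blocks on ID and high-school status, and its Aim 1 and 2 models leave both out. The consequence is lost precision of unknown size. A reader should not infer biased main effects from this or from the WASI-II change.

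The secondary point is conditional. It matters only if a WASI-II score is used as a moderator. For a continuous score the interaction would be multiplied by about 0.87 to 0.98, or 1 to 12 points off a nominal 80% power. This rests on assumed values of ρ and w and on taking the four-subtest score as the reference.

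**What to change.** 1. **Aims 1 and 2.** Add ID and high-school status, as recorded at randomisation, as covariates beside site and sex. State whether their effects may vary with time; for the treatment-by-time contrast in the linear models, they should. The data are already held. The cost is SAP wording and 2 d.f. for the main effects, plus a few more for the time terms.
2. **Aim 4, ID yes/no.** Use the same recorded ID block as the binary moderator and state how it was determined. If it was derived from the WASI-II, it carries the form change too, and the SAP should say so.
3. **Aim 4, continuous score.** If a WASI-II score is used, either add a term for test form, with its own interaction with treatment by time, or report a sensitivity analysis scoring everyone on the two common subtests. The common score is a trade-off: comparability improves, but under the formula above the multiplier becomes ρ for all families. With ρ = 0.90 and w = 0.50 it falls from 0.95 to 0.90. It therefore suits a sensitivity analysis better than the main one. The cost is re-scoring existing data; no new collection is needed.
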